The high pain monitoring model is based on the pain monitoring model which has been previously used in many studies. The difference is that the pain during exercise is higher than in the previous studies until the 9th week, with certain caveats: 1) during the exercises, the patient should feel discomfort/pain exceeding the pain at rest, ranging between 4 and 7 on NPRS (Numeric Pain Rating Scale). During the last set of 10/15 repetitions pain should not exceed 7; 2) Discomfort/pain should return to baseline level after 1 hour; 3) Discomfort/pain should not increase from day to day. In the last phase of the treatment (between 9th and 12th week) the pain during exercise ranges between 0 and 2 on NPRS, in order to allow the patient to focus on more proprioceptive and sport/work related tasks. A preliminary analysis of the data on 6 patients at the 6-week follow-up showed that all the subjects attended at least 4/6 physiotherapy sessions and they were all adherent to the home exercise (at least 10/11 home exercises completed) except one patient. Two patients experienced a slight increase (1 point on NPRS) in the level of pain after the physiotherapy or home exercise in the first three weeks. Discussing with both physiotherapists and patients, this was related to an increased level of sport in the same period or due to additional treatment of the posterior capsule, which can provoke initially some pain. The physiotherapist adapted the exercise and from the 4th week onwards the pain decreased to initial levels after 1 hour of exercise. Moreover, it emerged that a measurement of the pain after 1day was necessary to evaluate the evolution of the pain after painful exercises. This will be added in the design of the RCT and it is also in line with the recent recommendation for evaluating pain during and after exercises.

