# WP2: Randomized controlled trial

#### Design

This study will be conducted as an experimental randomized, controlled, doubleblind trial (RCT) in one physiotherapy practice in Belgium. The patients with SSP will be randomized into one of 2 groups (concealed, permuted block randomization of 2,4,6 size using randomisation.com), being either exercising into discomfort (G1) or exercising with slight/no discomfort (G2).

All training sessions will be applied for 12 weeks, three times weekly. The time points of assessment will be: before the start of the treatment (TO), at 6 weeks (T1), 12 weeks (T2), 26 weeks (T3). All participating patients will follow the flowchart illustrated in Figure 1.

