**Shoulder strength and Range of Motion (ROM)**: Shoulder strength is measured as isometric strength measurements with handheld dynamometer (IsoForce Dynometer EVO2; Medical Device Solutions AG) in abduction external rotation and scapular plane elevation. ROM in active and passive abduction and external/internal rotation will be determined with a goniometer (HALO digital goniometer; HALO, Medical Devices). These devices are already available at the University of Antwerp.

**Shoulder related Quality of Life**: Health-related Quality of Life index and Health-related Quality of Life VAS, measured with the EQ-5D-5L .

**Adherence:** The pain and the amount of exercise performed will be recorded in an exercise and pain diary. The participants will be asked to complete a pain diary, reporting pain on the VAS scale before and 1 hour and 1 day after each training session as well as the home training. Adherence will be analysed in terms of compliance with self-reported exercise diary: good compliance is defined by attendance of 6/9 supervised sessions and 80% of 27 home exercises.

**Fear of pain questionnaire-9 and Fear-Avoidance Beliefs Questionnaire (FABQ)**: these outcomes allow qualitative analysis of which patient characteristics (i.e. high level of anxiety and fear associated with pain) undermine compliance in case low adherence is observed. These questionnaires are both psychometrically sound and validated in Dutch.

**Other relevant outcomes**: Patients fill out the global perceived effectiveness (GPE) rating (1-much worse, 2-slightly worse, 3-no change, 4-slightly better, 5-much better) after the first session, at 6 and 12 weeks .

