### WP2: RCT

The RCT started in July 2020 and is still on going. In the initial FWO application the aim was to start the recruitment in April 2020 and to complete it by April 2021, with the final follow up in October 2021 (6 month after baseline assessment). A change to the timeline and sample size was necessary because of the low recruitment rate during the pandemic of Covid-19. The recruitment rate during the feasibility study before the pandemic (November 2019-February 2020) was 4-5 patients/month. The recruitment rate during the RCT was: 2.6 patients/month during the first year (July 2020-July 2021) and then 1.2 patient/month in the following 6 months (August 2021-January 2022). Fifty-four patients were included in the initial sample size calculation, estimating 15% of drop-out, power=90% and minimal clinically important difference (MCID)=8 points on the primary outcome SPADI. We planned to recruit patients until May 2022, aiming to 44 patients, with the last follow up measure in November 2022. Forty-four patients will still allow to have a well-powered study (85%) with MCID=10 points, which is considered in the range 8-13 points of the MCID in SPADI (Roy JS, MacDermid JC, Woodhouse LJ. Measuring shoulder function: a systematic review of four questionnaires. Arthritis Rheum. 2009;61(5):623-32). The extended time for data analysis in 2023 will allow the PhD student to conduct a thorough data analysis of objective and subjective data (see "Data analysis for 2nd term"). Status: 42 patients were recruited by the end of April 2022.

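### Adherence is recorded session by session, but the only analysis the plan defines is one joint good-compliance category, with no between-group estimate of sessions completed

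*Combined protocol and SAP*

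**What the plan says.** Under Outcome measures, adherence appears among the secondary outcomes. The recording is quantitative: "The pain and the amount of exercise performed will be recorded in an exercise and pain diary". The analysis sentence reads "Adherence will be analysed in terms of compliance with self-reported exercise diary", and the definition that follows is "good compliance is defined by attendance of 6/9 supervised sessions and 80% of 27 home exercises". The two thresholds are joined, so a patient must meet both. No reason is given for the cut.

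The denominators agree with the schedule under Design, "All training sessions will be applied for 12 weeks, three times weekly": 12 × 3 = 36 = 9 + 27.

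The section WP3: Data analysis applies the mixed model to SPADI, strength, range of motion and ultrasound parameters. Adherence is not among them; beyond the model, the section promises only suitable descriptive statistics. The 2022 renewal sets the target at "aiming to 44 patients, with the last follow up measure in November 2022" and adds nothing on how adherence is analysed.

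**The concern.** The category merges patients who differ a great deal. Eighty per cent of 27 is 21.6, so the home threshold is 22 sessions. Given enough supervised sessions, 22 home sessions count the same as 27, and 21 count the same as none.

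This matters because the trial compares exercise that provokes pain with exercise that hardly does. If SPADI shows no difference, readers will ask whether discomfort does not help or whether G1 simply exercised less. If SPADI favours G1, they will ask whether patients kept to the programme. A single yes/no class in about 44 patients answers either question only roughly, although the diary holds finer data.

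**Working it through.** **The plan's own figure.** There is none for adherence. The only power statement at 44 patients concerns SPADI: "Forty-four patients will still allow to have a well-powered study (85%) with MCID=10 points". It cannot be rebuilt, because no standard deviation or correlation is given, and it does not bear on adherence.

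**Inputs from the documents.** 44 patients, taken as 22 per arm (1:1 assumed); 15% dropout, giving about 19 per arm (44 × 0.85 = 37.4); 5% significance level (two-sided assumed); thresholds of 6/9 and 22/27.

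**Assumed inputs.** Attendance levels, between-patient overdispersion and pattern of non-adherence. The documents give none of these for the RCT.

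**Step 1: precision of the category.** At 80% good compliance in both arms, the half-width of the 95% interval for the difference is 1.96 × √(2 × 0.8 × 0.2 / 22) = 0.236, about ±24 percentage points.

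**Step 2: power of the category.** The normal approximation is Φ{(|p₁ − p₂|√n − 1.96√(2p̄q̄)) / √(p₁q₁ + p₂q₂)}. For 80% against 60% with n = 22: (0.938 − 1.270) / 0.632 = −0.525, so power is 30%.

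| G2 vs G1 good compliance | 22 per arm (Fisher) | 19 per arm (Fisher) |
|---|---|---|
| 80% vs 70% | 11.5% (7%) | 10% (6%) |
| 80% vs 60% | 30% (21%) | 26% (18%) |
| 80% vs 50% | 55% (43%) | 49% (40%) |
| 80% vs 40% | 79% (69%) | 73% (65%) |

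**Step 3: category against session counts.** Simulation with 22 per arm. Supervised (of 9) and home (of 27) counts are beta-binomial with overdispersion 0.1, 0.2 and 0.3, and a patient-level correlation of 0.5 between them. The yes/no test is chi-square; the count test is Welch on total sessions. Three patterns were tried:

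- *Uniform fall.* G2 85% supervised and 90% home, or 0.85 × 9 + 0.90 × 27 = 31.95 sessions. G1 75% and 80%, or 28.35 sessions.
- *Fall mostly above the cut.* G2 95% and 97% (34.74 sessions); G1 88% and 90% (32.22 sessions).
- *Early stopping.* Base 90% and 95% in both arms, with 30% of G1 stopping after 10-60% of their sessions.

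| Pattern | Yes/no power | Welch power |
|---|---|---|
| Uniform fall | about 30-53% | about 43-78% |
| Mostly above the cut | about 30-34% | about 46-83% |
| Early stopping | about 48-62% | about 74-82% |

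With equal arms, rejection rates stayed near the nominal 5%.

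**Step 4: choice of count method.** A Wilcoxon test gave 81/63/51% (overdispersion 0.1/0.2/0.3) under the uniform fall. Under early stopping it gave 42/41/43%, below the yes/no test at 62/49/48%, while Welch gave 82/79/74%. Only the difference in means beat the category in all three patterns.

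**The case against.** Several objections are fair, and most of them stand.

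- **No yes/no test is in the plan.** A reader might infer that adherence will be tested as a binary outcome and that counts will go unreported. The documents say neither. They define one category and name no between-group method. The team's feasibility reporting does use counts: "they were all adherent to the home exercise (at least 10/11 home exercises completed) except one patient". What stands is that no count analysis is specified for the RCT.
- **No power is claimed.** Adherence is in none of the four objectives' hypotheses, and the sample size rests on SPADI. Low power for a secondary process measure is not a design error, and nothing in the plan says that similar compliance will be concluded from a non-significant result.
- **A large pain-driven fall may be unlikely.** The feasibility patients followed the painful modality, and five of six did at least 10 of 11 home exercises. The renewal also reduced the painful exercises from four to one. Six patients are thin evidence, and a smaller fall above the cut is one that the category registers poorly.
- **Counts are not better under every method.** Step 4 shows that a rank test can lose to the category when some patients stop early. This decides which count analysis to use.
- **Small numbers limit any analysis.** Welch power is also below 80% in many settings.
- **The link to the fear questionnaires is inferred.** A reader might infer that failing the cut triggers that analysis. Outcome measures makes it conditional on observing low adherence, without saying that the category defines this.

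**Conclusion.** The point holds as a low-severity improvement. The plan collects session-level adherence and then defines only one joint category, with no count analysis and no between-group estimate. Under the assumed patterns, at 22 per arm, a difference in mean sessions has clearly more power than the category: about 43-78% against 30-53% for a uniform fall, 46-83% against 30-34% for a fall mostly above the cut, and 74-82% against 48-62% for early stopping. The size of the gain depends on attendance levels, overdispersion and dropout pattern, none of which the documents supply.

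The documents do not support the stronger reading that the planned analysis would hide any real fall in adherence. A fall in good compliance from 80% to 40% would probably be seen (79% power by chi-square). Nor would counts guarantee detection of a moderate fall.

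**What to change.** In the Adherence paragraph under Outcome measures:

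1. Make total sessions completed of 36 the one main adherence measure. Report it by group for all randomised patients, as a difference in means with a 95% confidence interval (Welch or bootstrap).
2. Give supervised (of 9) and home (of 27) counts as supporting descriptions.
3. State that patients who stop early contribute the sessions they completed. Treat unreturned diaries as missing, and report them separately from sessions not done.
4. Keep good compliance as a percentage by group.
5. Relate fear-of-pain and FABQ scores to the session count as well as to the category.

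The cost is a few sentences and a little analysis time. The diary already records the amount performed, so no patient, visit or treatment changes. The renewal puts unblinding at the end of the trial in November 2022; on that timetable the wording can be settled before group data are seen. The small downside is that a difference in sessions is less simple to quote than a percentage compliant, which stays in the table.

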# WP3: Data analysis

Statistical analyses will be performed using JMP ®Pro 14.0.0 (SAS Institute Inc., Cary, NC, USA) . Level of significance is set at p= 0.05. Appropriate descriptive statistics will be performed.

**OBJECTIVE 1,2,3:** A mixed regression model for repeated measures will be used to assess both the evolution of SPADI (pain and function), strength, ROM and US parameters within persons from baseline (T0) over time (T1, T2, T3) and the differences in evolution between subjects. Potential confounders are: age, gender, BMI, previous corticosteroid injections, severity of initial symptoms. They will be measured during the history taking at the first assessment and added into the mixed regression model as co-variants. If for a certain variable the percentage of missingness will be more than 15%, multiple imputation for missed observation will be used. There are three assumptions for the mixed regression model: change over time, a sensible measure for time (multiple time points of measure), normality of residuals (it will be checked using a Shapiro-Wilk test). If these residuals are not normally distributed, an appropriate transformation will be performed first. Therefore, this model best fits the longitudinal design of the RCT. **OBJECTIVE 4**: correlation analysis between tendon structures and clinical symptoms using the correlation for pairs of continuous variables in JMP.

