### Sample size

The sample size calculation was made using the Edland method, R package longpower 1.0-

11, based on the following data: 8% points as smallest clinically important difference in SPADI , 15% of estimated drop-out (as mean of dropout rates from previous studies ) and 30% for adjustment

for non-linearity of the data (since there is usually a higher decrease in SPADI in the first 3 months compared to 6 months). Considering a mixed regression model for repeated measures and using a moderate effect size (corresponding to 8% as smallest clinically relevant difference), confidence level at 5%, and power at 90%, the required total sample size is **54 subjects**, taking into account 15% dropout rate. The variance of the residuals cannot be estimated from previous studies, but it has a very limited effect on the sample size. It does not change the result of the power calculation, and therefore it is not included in this analysis.

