# Outcome measures

All outcomes will be measured at baseline (T0) and 6 (T1), 12 (T2), 26 (T3) weeks and the assessors will be blinded to group allocation. The **primary outcome** is the **difference in mean change between groups from T0 to T1, T2 (12 weeks, end of the treatment), and T3 (26 weeks, follow-up)** in the patient self-reported outcome score **Shoulder Pain and Disability Index (SPADI)**. This questionnaire is a patient-reported outcome measure (PROM) with high test–retest reliability and construct validity  and is available and validated in Dutch .

Secondary outcomes are registered for each patient at the same time points as the primary outcome, except for the Global Perceived Effect Score, which will be assessed after 1st treatment and then at 6 and 12 weeks. The secondary outcomes are:

**Scapular dyskinesis:** The procedure we will use is based on the procedures described by Tate et al.  and Struyf et al. . Scapular position will be observed at rest and during active loaded and unloaded humeral motion in a frontal and sagittal plane. The effect of scapular correction will be tested by means of the modified scapular assistance test and scapular retraction test . Reduction of pain during these tests compared with non-assistance during the same tests confirms scapular involvement in the shoulder complaints.

**Subacromial space**: Acromiohumeral distance (AHD) is a US measurement used to quantify the subacromial space. It is defined as the shortest linear distance between the most inferior aspect of the acromion and the humeral head . AHD is measured at 0 and 60 degrees of active shoulder elevation in the scapular plane, following the procedure of measurement indicated by Navarro-Ledesma et al . It has already been used to evaluate different populations, such as healthy volunteers  and patients with shoulder pain .

**Tendon changes**: Tendon structural changes (limited to RC thickness and long biceps) will be evaluated using US device and following international guidelines . STT will be also computed as percentage of subacromial space, known as the occupation ratio (using the formula [(STT/AHD)\*100] .

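### A Shapiro-Wilk test can move the primary SPADI analysis onto an unnamed transformed scale, and the plan keeps no primary analysis in SPADI points

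*Combined protocol and SAP*

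**What the plan says.** All of this is in the Combined protocol and SAP.

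- **WP3: Data analysis (application).** One model serves Objectives 1 to 3: "A mixed regression model for repeated measures will be used to assess both the evolution of SPADI (pain and function), strength, ROM and US parameters". Normality of its residuals is listed as an assumption, and "it will be checked using a Shapiro-Wilk test". The consequence is "If these residuals are not normally distributed, an appropriate transformation will be performed first". SPADI is not exempted. The section does not name the transformation, the kind of residual (marginal or conditional), a threshold for the test, a back-transformation, or an untransformed analysis that stays primary. The general rule is "Level of significance is set at p= 0.05".
- **Outcome measures.** SPADI is primary, and the quantity to be estimated is worded as follows: "difference in mean change between groups from T0 to T1, T2 (12 weeks, end of the treatment), and T3 (26 weeks, follow-up").
- **Sample size.** The target is "8% points as smallest clinically important difference in SPADI".
- **WP2: RCT (2022 renewal).** The target is revised: "Forty-four patients will still allow to have a well-powered study (85%) with MCID=10 points".

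The renewal does not alter the transformation rule.

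**The concern.** The outcome definition and both sample-size statements are in SPADI points. The analysis rule lets a significance test on the residuals decide whether the model is fitted in points at all. If the test rejects, the group-by-time term on the new scale is no longer the stated primary outcome, and the plan does not say how it would be turned back into points.

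The choice of transformation is also open. Residuals exist only once a model has been fitted, so the untransformed result can be known before a transformation is picked. At stake are the quantity the trial reports as its main result, its link to the clinical target, and to a smaller degree whether p falls below 0.05.

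**Working it through.** **1. The plan's own figures.** The totals of 54 (8 points, 90% power) and 44 (10 points, 85% power) cannot be reproduced, because no SPADI standard deviation or slope variance is given. This point does not depend on them. What matters is that both are stated in points.

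**2. Scale, with no assumption about variance.** Take two pairs of group means, each 10 points apart:

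| Means | Difference | Ratio | Log ratio | Difference in square roots |
|---|---|---|---|---|
| 50 vs 40 | 10 | 40/50 = 0.80 | ln 0.80 = -0.22 | 7.07 - 6.32 = 0.75 |
| 20 vs 10 | 10 | 10/20 = 0.50 | ln 0.50 = -0.69 | 4.47 - 3.16 = 1.31 |

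The same 10 points gives different effects on either scale, depending on where the patients are. A log or root estimate therefore has no fixed equivalent in points to set against 8 or 10.

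**3. How often the rule could act, and change the conclusion.** None of the distributional inputs is in the documents, so all are assumed:

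- 44 patients, 1:1, a true 8-10 point effect, and both tests at 0.05.
- Clipped scores: normal scores cut off at 0, with mean SPADI of 40-50 falling to 15-25, between-patient SD 10-14 and within-patient SD 10-12.
- A second set of runs: means 45, 30, 20 and 15 at the four visits, SD 12 or 16, within-patient correlation 0.5, and either clipped normal or right-skewed (gamma) scores.
- The group comparison is a T0-T2 change score, or T2 adjusted for T0. Both are simpler than the planned four-visit model.

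For the clipped scores, Shapiro-Wilk rejects in about 5-14% of trials with conditional residuals and 8-57% with marginal residuals. In the second set, with marginal residuals, it rejects in 17-48% of clipped-normal trials and 97-100% of right-skewed trials.

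The relevant event is that the test rejects **and** the raw and transformed analyses fall on opposite sides of 0.05. For clipped scores, two separate sets of runs gave:

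| Residuals and comparison | Log, first set | Log, second set | Square root, first set |
|---|---|---|---|
| Conditional, change score | 2.7-4.9% | about 1-2% | 2.0-4.0% |
| Conditional, adjusted for T0 | 1.3-2.3% | about 0.5-1.4% | 0.7-1.6% |
| Marginal, change score | 8.7-19.4% | about 6-21% | 6.1-14.9% |
| Marginal, adjusted for T0 | 4.5-11.3% | about 4-14% | 3.1-8.3% |

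With right-skewed scores included (marginal residuals, T2 adjusted for T0), the joint rate is 3.2-17.6% for log and 1.5-11.4% for square root.

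**4. Direction.** For 8 points and SD 12, power with right-skewed scores is 71% raw, 82% square root and 88% log. With clipped-normal scores it is 68%, 66% and 59%. Transformation can help or hurt.

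**5. Is the transformation needed for validity?** With no true effect, the raw-scale test rejects in 4.4-5.6% of trials across the runs. With a transformation fixed in advance the figure is 4.5-5.6%. If the best of raw, log, square root and rank is picked after Shapiro-Wilk rejects, it is 5.4-7.8%.

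**The case against.** The case on the other side is substantial on size.

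- **The rule is conditional.** A reader who compares raw and transformed change-score analyses in every simulated trial finds disagreement in about 27-30% (log) or 17-21% (square root), and might infer that this is the risk of a changed result. It is not. The plan transforms only when the test rejects, so only the joint rates above apply. This objection stands in full.
- **Log may not count as appropriate.** With clipped scores, when raw residuals failed, log(y+1) residuals failed too in 86-100% of trials. Trials where the test rejected, log passed and significance differed were at most 0.7% (square root 1.3-7.1%). This stands for that distribution, if an appropriate transformation is one that passes the test. The plan does not say so, and right-skewed scores could behave differently.
- **Non-normality may be slight.** A reader might infer that the floor at 0 makes rejection near certain. The documents give no means or standard deviations to support that, and with conditional residuals the assumed rejection rate starts at the nominal 5%.
- **Error control is little affected.** A reader might infer a materially inflated type I error. A transformation fixed in advance shows none, and picking the best of four analyses takes it to 7.8% at most. Nothing in the documents suggests that the team intends to pick by p value.
- **Points could still be shown.** The plan promises descriptive statistics and does not rule out back-transformation, so it goes too far to say that a transformed result could tell nothing about clinical relevance. But neither of these promises the covariate-adjusted difference in mean change in points.

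**Conclusion.** The point holds, chiefly as one about what is estimated. Followed as written, the rule can replace the stated primary outcome with an effect on an unnamed scale that cannot be read directly against 8 or 10 points. That conclusion follows from the text and simple arithmetic, and does not depend on any assumed SPADI distribution.

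The effect on significance is secondary and uncertain. For clipped scores it is about 1-5% of trials with conditional residuals and about 4-21% with marginal residuals, falling to as little as about 0.5% with conditional residuals and baseline adjustment, and generally lower with a square root. These ranges rest on assumed means, standard deviations and shapes, and on a simplified two-visit comparison. Raw-scale type I error near 5% in these settings means that little is lost by staying in points. The change should be made, but the flaw does not invalidate the trial.

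**What to change.** In WP3: Data analysis, state for SPADI that:

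1. the mixed model on the untransformed percentage scale (0-100) is the primary analysis whatever the Shapiro-Wilk result;
2. a robust-variance or bootstrap confidence interval for the same mean difference in points is always reported as a supporting analysis, not only when residuals look skewed;
3. any transformation is one named in advance and serves only as a sensitivity analysis.

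The existing rule may stay for the other outcomes.

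The cost is about a sentence of text and one extra run, with no new data and no change in sample size. The renewal's WP3: Data analysis places unblinding at the end of the trial in November 2022, so the wording should be fixed before the group codes are opened.
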